## **PROTECTION OF HUMAN SUBJECTS**

### **1. Risks to Human Subjects**

#### **a) Human subjects involvement and characteristics**

As described in the research plan, we will recruit 75 youth ages 13-17 to participate in this study. Children will be involved in this study, given that the specific aims of the study pertain to animal-assisted interventions for adolescents with social anxiety. This age range was selected due to the importance of adolescence as a critical period for the development of social anxiety.

Participants will be recruited via stratified sampling defined by scores on the Social Anxiety for Adolescents scale (SAS-A; La Greca & Lopez, 1998). We aim to recruit 25 participants in each of three strata as defined by scores of >50 (high anxiety), 36-50 (mid anxiety), and <36 (low anxiety) as recommended by La Greca (1999). Exclusion criteria include self-reported fear of or allergy to dogs. There are no exclusion criteria based on sex or race/ethnicity.

Eligible participants will be randomized into one of three conditions: 1) control group (no contact with a therapy dog); 2) social interaction with a therapy dog (no physical contact); and 3) social + physical interaction with a therapy dog. Participants in all three conditions will complete the validated Trier Social Stress Task for Children (TSST-C), which involves a public speaking task and a mental arithmetic performance challenge. During the experiment, participants will wear a clinical grade wearable sensor (similar to a watch). They will be asked to complete a self-report questionnaire of their anxiety level at baseline (State-Trait Anxiety Inventory – State scale; STAI), during each portion of the TSST-C, and at the end of the experiment. All sessions will be video recorded.

Each potential participant will be given a \$10 gift card to complete the screening process (approximately 15 minutes, can be completed at home via digital screening tool). Youth who meet the eligibility criteria will be invited to participate in the full experiment (approximately 2 hours), and will be compensated with a \$75 gift card as an incentive for participating in the study and for travel expenses (\$50 for participation, \$25 for travel costs). This compensation rate is necessary given the specific nature of our target sample and the time investment on the part of the participants, including travel to Tufts University.

#### **b) Sources of Materials**

This project will involve four primary sources of data: (1) survey data, (2) heart rate physiology data, (3) performance data, and (4) video recording of behavior.

Prior to any data being collected, parents will be asked to read a permission form to consent to their child's participation. Children will receive an assent form before completing the eligibility screening process.

##### *1. Survey Data*

Online questionnaire data for the screening survey will be conducted through the Tufts University CTSI REDCap system, and REDCap will be used for storing all study data. REDCap allows identifier data to be flagged as sensitive, and has advanced utility for restricting access and downloading de-identified data for analysis. REDCap is HIPAA-compliant with high security (protected behind the Tufts Medical Center firewall, servers housed in a secure local data center, all web-based information encrypted). For practical reasons, it is necessary to store participant identifiers with screening data within the REDCap system. Data and identifiers will only be accessible to authorized study personnel (PI, Co-Is, and staff research assistant; not accessible to student research assistants).

In addition, participants will complete the self-report anxiety scale (STAI) during the experiment through an online survey on an iPad. The STAI survey will be administered through Qualtrics (Tufts University account), a secure, encrypted survey platform ensuring protection of data. Survey data will be password-protected through the secure platform.

The PI will randomly assign a four digit ID number to each participant (through a randomized variable creation command in Microsoft Excel). The survey data files will be downloaded onto a Tufts University secure server as an SPSS file without identifiers. All identifiers (including the key ID file) will be stored securely in REDCap.

## *2. Heart Rate Data*

Heart rate and electrodermal conductance data from the wearable heart rate monitor (Empatica E4) will be downloaded from the watch directly to a password-protected (Tufts security) Box folder. The file will be password protected and will only contain the participant's ID number (no identifying information), and will only be accessible to the PI and Co-Is.

## *3. Performance Data*

Performance during the mental arithmetic portion of the TSST-C (number of errors and lowest number reached) will be recorded securely in REDCap.

## *4. Video Data*

All sessions will be video recorded to code for social referencing behaviors between participants and the therapy animals. Video files will be downloaded immediately from the camera's USB drive (and subsequently deleted from the camera) and stored in a password-protected file on a secure Tufts University server. Two copies of each video file will be stored on the Tufts server as backup in case of file corruption, and will be retained for five years. The video data will be coded with each participant's unique four-digit ID code. Behavior coding will be quantified and stored in a password-protected NVIVO file that contains only the participants' ID numbers. The PI, co-investigators, and research assistants participating in behavior coding will be the only individuals with access to the video data. All study personnel will be CITI-certified and approved by the Tufts University Institutional Review Board.

### **c) Potential Risks**

Given the content of the questions and data collection methodologies, we anticipate minimal risk to participants. Answering questions about personal feelings and participating in the social stressor situation as part of the Trier Social Stress Task may have risk of causing emotional distress, particularly for participants who are experiencing high levels of social anxiety. The TSST-C has been well-validated for use in youth populations (Buske-Kirschbaum et al., 1997; Stroud et al., 2009) and has been widely used without causing undue risk to participants. For participants who are randomized to the conditions that involve interacting with a dog, there is always minor risk associated with interacting with live animals.

## **2. Adequacy of Protection Against Risks**

### **a) Recruitment and Informed Consent**

Participants will be recruited from the Massachusetts area by leveraging advertisement through Tufts University resources (e.g., Tufts University School of Medicine, existing contacts through the Tufts Paws for People group, local clinics and educational programs). Flyers and email announcements will be sent to relevant listserves.

Consent for completing the brief online screening tool will be obtained digitally. Upon clicking on screening survey link, parent will be asked to complete a permission form for their child's participation. After parental consent/permission is received, the survey will direct to an assent form that youth will be asked to read and respond to. If youth agree to participate in the screening survey, they will then be directed to the survey.

For participants who are eligible to participate in the experiment, parental consent and youth assent will be obtained in person. A CITI-certified researcher will explain the nature of the study, and the risks, and parents/guardians will be asked to respond to a hard copy consent form. If the parent consents, then the youth participant will be asked to read and respond to a similar assent form. All participants and their parent/guardian will be reminded that they can choose to not participate in the study without any consequences, and that they may discontinue at any time once the study has begun.

### **b) Protection Against Risks**

As noted above, there are minimal risks associated with this study. Although risks are minimal, we will provide participants with the PI's contact information should any questions or concerns arise, as well as provide contact information for mental health resources. We will also highlight the participant's right to discontinue his or her participation in any part of the study (including the TSST-C) at any time. If a participant becomes distressed during the TSST-C, the study will be stopped immediately, and the participant and his or her parent/guardian will be provided with contact information for a mental health professional.

As noted above, confidentiality of digital data will be maintained by assigning a four digit ID number to each participant that will be stored securely in REDCap. De-identified data files and video data files will be stored on a secure Tufts University server and will only be accessible by the PI and the co-investigators.

The animals participating in this study will be therapy dogs who are registered through Pet Partners® and members of Tufts Paws for People, reducing the risk of adverse events. The animals will always be accompanied by their handlers, who are required by Pet Partners to have their dogs on leash at all times while visiting and have been trained to advocate for their animals to ensure safety of all participants. As part of their Pet Partners training, all animal handlers have completed an 8-hr training course and their animals have passed a rigorous evaluation (with re-evaluation every 2 years) to meet training, safety, and health standards that protect both the animal-handler team and the people and facilities they are visiting. The animals are bathed 24 hours prior to participating in any program, and the teams are covered by comprehensive liability insurance through Pet Partners.

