## Measures

To test the mechanism of action for canine interaction in reducing social anxiety in adolescents, we will collect three levels of outcome data: a) self-reported experience (anxiety), b) autonomic physiological reactivity (heart rate), and c) cognitive performance (error rates on mental math task).

*Social anxiety.* The SAS-A will be used to assess overall level of social anxiety. The SAS-A was designed for use in adolescence and has been validated extensively across many samples and in multiple languages (e.g., Garcia-Lopez et al., 2011; La Greca & Lopez, 1998). The SAS-A contains 18 items that include three domains of social anxiety: fear of negative evaluation from peers, social avoidance and distress in new situations, and generalized social avoidance.

*Self-Report Experience:* Self-reported affective experience will be measured using the state scale of the State-Trait Anxiety Inventory (STAI; Spielberger et al., 1983), which is validated for use in adolescence and is commonly used with the TSST. The STAI state scale contains 20-items rated on a four-point scale, and has consistently demonstrated excellent reliability (ranging from  $\alpha = .86$  to  $.95$ ; Spielberger et al., 1983) and construct validity (Spielberger, 1989). Anxiety will be measured at six time points, during: (1) baseline, (2) anticipation (3) preparation, (4) speech, (5) mental math, and (6) recovery.

*Autonomic physiological reactivity:* Heart rate and electrodermal activity will be collected continuously using a clinical grade wristband sensor (Empatica E4; Garbarino et al., 2015).

*Cognitive Performance:* Cognitive performance during the social stressor task will be measured to understand how anxiety and AAI influence cognitive function. As recommended by existing research with the TSST paradigm (e.g., Simeon et al., 2007), we will measure cognitive performance during the mental arithmetic task by tracking the number of errors and lowest number reached by participants on the mental math task. Better performance will be characterized by fewer errors and reaching a lower number during serial subtraction.

*Demographic Characteristics:* In addition to the measures assessing the primary aims, we will also collect demographic covariate information from participants on age, sex, race/ethnicity, and current pet ownership.

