### **5. Data Safety and Monitoring Plan**

**Safety Monitoring:** Given the content of the questions and data collection methodologies, we anticipate minimal risk to participants. Answering questions about personal feelings and participating in the social stressor situation as part of the Trier Social Stress Task may have risk of causing emotional distress, particularly for participants who are experiencing high levels of social anxiety. The TSST-C has been well-validated for use in youth populations and has been widely used without causing undue risk to participants. For participants who are randomized to the conditions that involve interacting with a dog, there is always minor risk associated with interacting with live animals.

Although risks are minimal, we will provide participants with the PI's contact information should any questions or concerns arise, as well as provide contact information for mental health resources. We will also highlight the participant's right to discontinue his or her participation in any part of the study (including the TSST-C) at any time. If a participant becomes distressed during the TSST-C, the study will be stopped immediately, and the participant and his or her parent/guardian will be provided with contact information for a mental health professional. If any minor skin irritation or discomfort takes place as a result of wearing the E4 wristband, it will be removed immediately.

The animals participating in this study will be therapy dogs who are registered through Pet Partners® and members of Tufts Paws for People, reducing the risk of adverse events. The animals will always be accompanied by their handlers, who are required by Pet Partners to have their dogs on leash at all times while visiting and have been trained to advocate for their animals to ensure safety of all participants. The animal handlers are trained to recognize stress signals in their dogs and will discontinue participation immediately if the therapy animal becomes stressed.

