### *Analyses:*

To test our confirmatory hypotheses, we conducted two three-way analyses of variance (ANOVA) with either self-reported anxiety (STAI), autonomic reactivity (electrodermal activity [EDA] and heart rate [HR]) as the dependent variable. For these outcomes, there were two between-subjects factors, condition (social, social + physical, control) and social anxiety (SA; centered continuous predictor), and one within-subjects factor, time point (1, 2, 3, 4, 5, 6). We included baseline STAI, EDA, or HR at time point 1 as a centered continuous covariate. For cognitive performance, we conducted ANOVAs that treated condition as a between-subjects categorical factor and social anxiety as a centered continuous predictor.

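### Sessions that end early on distress would, under a conventional six-phase ANOVA, lose even the phases already recorded (minor)

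*Protocol*

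**What the plan says.** In the protocol section on protection against risks, the rule is: "If a participant becomes distressed during the TSST-C, the study will be stopped immediately". I read this as ending that participant's session, not the trial. The same section gives participants the "right to discontinue his or her participation in any part of the study (including the TSST-C) at any time". The data safety and monitoring plan repeats both provisions.

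The section on potential risks says "we anticipate minimal risk to participants". It adds that the questions and the stress task "may have risk of causing emotional distress, particularly for participants who are experiencing high levels of social anxiety". Baseline social anxiety is the moderator in Aim 2.

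Under Measures, "Anxiety will be measured at six time points": baseline, anticipation, preparation, speech, mental math and recovery. Heart rate and EDA are recorded continuously.

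The SAP's Analyses section uses condition and centred social anxiety as between-subject factors and "one within-subjects factor, time point (1, 2, 3, 4, 5, 6"). It continues: "We included baseline STAI, EDA, or HR at time point 1 as a centered continuous covariate". Neither document defines an analysis set, a rule for incomplete sessions or a count of stops by condition. The SAP's sample size section describes the step from 23 to 25 per group as rounding, not as an allowance for losses.

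**The concern.** A distress stop is close to being an event on the outcome scale, because the STAI and heart rate are there to measure the same state. If the dog lowers anxiety, stops should be more common in the control arm. The protocol itself expects distress to fall mainly on participants with high social anxiety, who matter most for Aim 2.

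A conventional repeated-measures ANOVA needs all six values from each person. Someone stopped during the speech already has baseline, anticipation and preparation STAI (3 of 6 scores), plus heart rate and EDA up to the stop. All of that would be discarded.

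Two things are at stake: some power, and a completer comparison from which the most anxious controls have been removed.

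**Working it through.** **1. The plan's own power.** Inputs from the SAP's sample size section: HR difference 12, SD 12; STAI difference 10, SD 10.5; alpha 0.05 (taken as two-sided, which is not stated). Method: two-sample t test with noncentrality d / (SD × √(2/n)) and 2n − 2 degrees of freedom.
- HR, n = 23: 12 / (12 × √(2/23)) = 3.39, power 0.912. At n = 22 it is 0.8997, so 23 reproduces.
- STAI, n = 25: 10 / (10.5 × √(2/25)) = 3.37, power 0.910. The stated 90% reproduces.

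**2. Power if whole participants are lost.** Same formula:

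| n per group | HR | STAI |
|---|---|---|
| 25 | 0.934 | 0.910 |
| 24 | 0.924 | 0.898 |
| 23 | 0.912 | 0.885 |
| 20 | 0.869 | 0.835 |

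One loss per group takes STAI just under 90%. HR stays above 90% until n = 22.

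**3. Direction and size of bias, STAI.** The documents give no stop rate, so this is illustration only. Assumptions: true difference 10 at phases 2-6, SD 10.5; correlation 0.5-0.7 between any two phases; a stop during speech when a distress score, correlated rho with speech STAI, passes one cut common to both arms.

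Unadjusted closed form at 12% control stops and rho = 0.5:
- Control cut c = 1.175. Completers' mean falls by rho × SD × φ(c)/Φ(c) = 0.5 × 10.5 × 0.2000/0.88 = 1.19.
- Dog arm cut: 1.175 + 0.5 × 10/10.5 = 1.651, so about 5% stop. Completers' mean falls by 0.5 × 10.5 × 0.1021/0.9506 = 0.56.
- Completer difference: 10 − (1.19 − 0.56) = 9.37.

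The planned baseline covariate recovers part of this. Large-sample simulation (1.5 million per arm), comparing baseline-adjusted completers with a mixed model that keeps phases 1-3 of stopped participants:

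| Control stops | rho | Phase | Completers | Mixed model |
|---|---|---|---|---|
| 12% | 0.5 | speech | 9.5-9.7 | 9.6-9.8 |
| 12% | 0.5 | preparation | about 9.85 | 10.0 |
| 12% | 1 (extreme) | speech | 8.5-8.9 | 8.7-9.15 |
| 12% | 1 (extreme) | preparation | 9.5 | 10.0 |
| 4% | 0.5 | speech | 9.8 | 9.8-9.9 |

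The mixed model is unbiased at preparation because that phase is fully recorded before the stop. At speech some bias remains, because the stop depends on a score that was never taken.

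**4. Scale.** The standard error of a two-group STAI difference is 10.5 × √(2/25) = 2.97, or 2.97 × √(1 − 0.6²) = 2.38 with an assumed baseline correlation of 0.6. At 4% control stops (one of 25 expected), the chance of seeing none is 0.96^25 = 0.36.

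**The case against.** The strongest reply is that this hardly matters. Risk is described as minimal, no stop rate is given, and at moderate correlation the mixed model gains about 0.1 STAI point against a standard error of 2.4-3.0. The bias runs against the study's hypothesis. The planned model also contains social anxiety, which should absorb a little more. With an assumed correlation of 0.5-0.8 between social anxiety and the stable person-level component, the speech gain at 12% stops falls to about 0.03-0.07 (rho 0.5). All of this stands, and it is why the point is minor.

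It is also true that the SAP names no software or estimation method. Whole-participant deletion is what a conventional fit does, not something the SAP states. That limits the claim but does not remove it, since a reader cannot tell who would be analysed.

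Three stronger readings are tempting and are not supported:
- A reader might infer a spurious dog benefit, because handlers "will discontinue participation immediately if the therapy animal becomes stressed" and this can occur only in the dog arms. The documents do not say that removing the dog ends the adolescent's session or loses data, and the trigger is the dog's stress, not the participant's score. Any loss rates would be invented.
- A reader might carry the speech-phase bias over to heart rate. Heart rate is continuous, so the part of the phase before the stop is recorded.
- A reader might conclude that the stop rule should be loosened. It should not. The gap lies in the analysis.

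**Conclusion.** The point holds, as a minor one. The protocol creates two routes to incomplete sessions, one of them tied directly to distress, and the SAP names an analysis that conventionally discards such sessions whole. The frequency is unknown and may be zero. If stops occur, STAI power slips below 90% after one loss per group. Completer bias is a few tenths of a STAI point at moderate correlation and 12% control stops, usually towards understating a dog effect. Larger figures need a distress score perfectly correlated with STAI. These sizes rest on the assumed stop rates, correlations and common stopping cut, none of which the documents give. The case for change is that keeping the recorded data costs almost nothing, not that the planned result would be seriously wrong.

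**What to change.** Leave the safeguard unchanged.

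1. Replace the repeated-measures ANOVA with a likelihood-based mixed model for repeated measures, with unstructured covariance and Kenward-Roger degrees of freedom, on all randomised participants in their assigned arm. Use phases 2-6 as outcomes and phase 1 as covariate only; the SAP now lists time point 1 as both. Keep social anxiety and its planned interactions. Include every phase recorded before a stop, and summarise heart rate and EDA in a partly recorded phase over the recorded portion.
2. Tabulate distress stops, voluntary discontinuations and dog removals by condition and phase, descriptively. Testing them would be uninformative: 3 of 25 against 0 of 25 gives Fisher's exact p = 0.23.

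A sensitivity analysis giving missed phases an unfavourable score is optional.

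Cost: SAP wording, one table and slightly more analysis work, with no new data and no added burden on participants. Some bias remains for STAI at the stopped phase. The Analyses section is written in the past tense; if the analysis has already been run, label the mixed model as a post hoc check. If no session was cut short, the table says so and the question is closed.

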### **3. Potential Benefits of the Proposed Research to Human Subjects**

There are no direct benefits to participants other than helping researchers better understand how contact with therapy animals may reduce anxiety for adolescents.

### **4. Importance of the Knowledge to be Gained**

The results of this research will provide important data exploring the mechanisms of action underpinning anxiety reduction in animal-assisted interventions (AAI). The proposed study will expand our knowledge about both if and how AAI can be an effective strategy for reducing social anxiety. Using novel and rigorous methods to address a fundamental question in AAI, this study represents theoretical, methodological, and translational innovations in AAI research. Overall, this award would allow us to better understand the processes involved in effective AAI. Given the potential benefits for understanding and promoting the potential positive impact AAI on anxiety, the benefits of this study outweigh the minor risks.

